6.5 Concomitant medication(s)/treatment(s)

6.5.1 Permitted concomitant treatments (medications and therapies)

6.5.1.1 Corticosteroids

Corticosteroids are permitted during the study at any dose in the sense of escape medication, if medically indicated (see Section 6.6.2). At the screening visit (V1) corticosteroid dose must not exceed 40mg/day prednisone equivalent and must be stable for 2 weeks prior to Screening (approximately 4 weeks prior to Baseline Visit). Further, the dose must remain stable during Screening Period and should be kept stable onwards, if possible, or tapered. In case of a high corticosteroid dose (>20mg/day) an early start of tapering should be considered depending on the individual patient's condition. If the corticosteroid dose exceeds 7.5mg/day prednisone equivalent, it should be tapered in line with international treatment guidance as soon as possible, but must be initiated at the latest at Week 8 (V4). The timepoint and speed of tapering should be adapted to the individual study participant's condition (see below). Steroid doses should be converted to prednisone equivalent doses prior to the assessment of study participant inclusion criteria and initiation of corticosteroid tapering (regardless of route, except for intraocular, nasal, and topical). The list of corticosteroids and their corresponding prednisone equivalent doses can be found in [Table 6-2](#).

Table 6-2: Prednisone equivalent doses of systemic corticosteroids

Corticosteroids	Prednisone equivalent dose to 1mg of the listed corticosteroid dose
Cortisone	0.2mg
Hydrocortisone	0.25mg
Deflazacort	0.75mg
Prednisolone	1mg
Prednisone	1mg
Methylprednisolone	1.25mg
Triamcinolone	1.25mg
Dexamethasone	6.7mg

Table 6-2: Prednisone equivalent doses of systemic corticosteroids

Betamethasone	8.3mg
---------------	-------

To determine the prednisone equivalent dose of the corticosteroids shown on the left, multiply the mg dose of corticosteroid on the left by the dose amount in the corresponding right hand column. For example, a 0.8mg dose of methylprednisolone is equivalent to 1mg ($0.8\text{mg} \times 1.25$) of prednisone.

The dose of a specified corticosteroid that is equivalent to 1mg prednisone is given in [Table 6-3](#).

Table 6-3: Corticosteroid dose equivalent to 1mg prednisone

Corticosteroids	Corticosteroid dose equivalent to 1mg prednisone
Cortisone	5mg
Hydrocortisone	4mg
Deflazacort	1.3mg
Prednisolone	1mg
Prednisone	1mg
Methylprednisolone	0.8mg

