Triamcinolone	0.8mg
Dexamethasone	0.15mg
Betamethasone	0.12mg

A pulse dose ($>500\text{mg} \times 1$ to 3 days) of iv corticosteroids should not have been given within the 4 weeks before screening.

Study participants not receiving concomitant corticosteroids or who were previously receiving corticosteroids on an as-needed basis must have stopped the treatment or been assigned to a continuous corticosteroid dose at least 2 weeks prior to Screening (Visit 1).

In study participants receiving concomitant corticosteroid doses $>7.5\text{mg/day}$ prednisone or equivalent, a mandatory corticosteroid taper must be initiated as early as possible but no later than 8 weeks after the first study medication infusion (Day 56). The tapering regimen will aim to reduce the daily prednisone equivalent dose to 7.5mg/day or lower by Week 18.

If such a rapid tapering is not considered by the Investigator to be appropriate for the individual study participant, a slower tapering regimen can be used.

Study participants achieving a dose of 7.5mg/day or lower may remain on this dose or continue to taper at the discretion of the Investigator. It is recommended to reduce the dose further in a slow manner.

Study participants whose disease is worsening after initiation of tapering and therefore cannot fulfill the taper based on the Investigator's judgment or whose corticosteroid dose has to be increased, if indicated, should remain in the study and receive corticosteroids at an appropriate

dose as determined by the Investigator. Study participants will be considered nonresponders for the primary endpoint in case of the intercurrent event escape treatment intervention with corticosteroids as outlined in Section 8.1.3.1.

Study participants will be issued a daily diary in which to record corticosteroid doses taken on a daily basis at home in between visits. Investigators are advised to contact the Medical Monitor or Sponsor's Study Physician upfront, if possible, to discuss the potential impact on the further study conduct in case use of oral or parenteral steroids for non-SLE related conditions is needed.

In case the corticosteroid dose at screening visit (V1) is not shown in the recommended tapering regimen table (Table 6-4), the tapering regimen of the next higher dose in the table should be used. Reduction of corticosteroids between Weeks 44 and 48 should be avoided.

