This document cannot be used to support any marketing authorization application and any extensions or variations thereof.

PUBLIC COPY

Table 6-4: Recommended corticosteroid tapering schedule

Week	Day	Corticosteroid dose ^a (mg/day; prednisone equivalent)										
Starting Dose		40 ^a	35 ^a	30 ^a	25 ^a	20 ^a	15 ^a	10 ^a	7.5 ^b	5 ^b	2.5 ^b	0
1	Day 1 to Day 7	30	30	30	25	20	15	10	7.5	5	2.5	0
2	Day 8 to Day 14	30	20	30	25	20	15	10	7.5	5	2.5	0
3	Day 15 to Day 21	20	20	20	20	20	15	10	7.5	5	2.5	0
4	Day 22 to Day 28	20	15	20	20	20	15	10	7.5	5	2.5	0
5	Day 29 to Day 35	15	15	15	15	15	10	10/7.5 ^{b,c}	7.5 ^b	5 ^b	NA ^b	NA ^b
6	Day 36 to Day 42	15	10	15	15	15	10	10/7.5 ^{b,c}	7.5 ^b	5 ^b	NA ^b	NA ^b
7	Day 43 to Day 49	10	10	10	10	10	10 ^b	10/7.5 ^{b,c}	7.5/5 ^{b,c}	5 ^b	NA ^b	NA ^b
8	Day 50 to Day 56	10	10	10	10	10	10 ^b	10/7.5 ^{b,c}	7.5/5 ^{b,c}	5 ^b	NA ^b	NA ^b
9	Day 57 to Day 63	10	10/7.5 ^{b,c}	10	10	10	10/7.5 ^{b,c}	7.5 ^b	7.5/5 ^{b,c}	5 ^b	NA ^b	NA ^b
10	Day 64 to Day 70	10/7.5 ^{b,c}	10/7.5 ^{b,c}	10/7.5 ^{b,c}	10/7.5 ^{b,c}	10/7.5 ^{b,c}	10/7.5 ^{b,c}	7.5 ^b	7.5/5 ^{b,c}	5 ^b	NA ^b	NA ^b
11	Day 71 to Day 77	10/7.5 ^{b,c}	10/7.5 ^{b,c}	10/7.5 ^{b,c}	10/7.5 ^{b,c}	10/7.5 ^{b,c}	10/7.5 ^{b,c}	7.5 ^b	7.5/5 ^{b,c}	5 ^b	NA ^b	NA ^b
12	Day 78 to Day 84	10/7.5 ^{b,c}	10/7.5 ^{b,c}	10/7.5 ^{b,c}	10/7.5 ^{b,c}	10/7.5 ^{b,c}	10/7.5 ^{b,c}	7.5 ^b	7.5/5 ^{b,c}	5 ^b	NA ^b	NA ^b

Table 6-4: Recommended corticosteroid tapering schedule

Week	Day	Corticosteroid dose ^a (mg/day; prednisone equivalent)									
13	Day 85 to Day 91	10/7.5 ^{b,c}	7.5 ^b	10/7.5 ^{b,c}	10/7.5 ^{b,c}	10/7.5 ^{b,c}	7.5 ^b	7.5/5 ^{b,c}	5 ^b	5 ^b	NA ^b
14	Day 92 to Day 98	7.5 ^b	7.5 ^b	7.5 ^b	7.5 ^b	7.5 ^b	7.5 ^b	7.5/5 ^{b,c}	5 ^b	5 ^b	NA ^b
15	Day 99 to Day 105	7.5 ^b	7.5 ^b	7.5 ^b	7.5 ^b	7.5 ^b	7.5 ^b	7.5/5 ^{b,c}	5 ^b	5 ^b	NA ^b
16	Day 106 to Day 112	7.5 ^b	7.5 ^b	7.5 ^b	7.5 ^b	7.5 ^b	7.5 ^b	7.5/5 ^{b,c}	5 ^b	5 ^b	NA ^b
17	Day 113 to Day 119	7.5 ^b	7.5/5 ^{b,c}	7.5 ^b	7.5 ^b	7.5 ^b	7.5/5 ^{b,c}	7.5/5 ^{b,c}	5 ^b	5 ^b	NA ^b
18	Day 120 to Day 126	7.5/5 ^{b,c}	7.5/5 ^{b,c}	7.5/5 ^{b,c}	7.5/5 ^{b,c}	7.5/5 ^{b,c}	7.5/5 ^{b,c}	7.5/5 ^{b,c}	5 ^b	5 ^b	NA ^b
19	Day 127 to Day 133	7.5/5 ^{b,c}	7.5/5 ^{b,c}	7.5/5 ^{b,c}	7.5/5 ^{b,c}	7.5/5 ^{b,c}	7.5/5 ^{b,c}	5 ^b	5 ^b	5 ^b	NA ^b
20	Day 134 to Day 140	7.5/5 ^{b,c}	7.5/5 ^{b,c}	7.5/5 ^{b,c}	7.5/5 ^{b,c}	7.5/5 ^{b,c}	7.5/5 ^{b,c}	5 ^b	5 ^b	5 ^b	NA ^b
21	Day 141 to Day 147	7.5/5 ^{b,c}	5 ^b	7.5/5 ^{b,c}	7.5/5 ^{b,c}	7.5/5 ^{b,c}	5 ^b	5 ^b	5 ^b	5 ^b	NA ^b

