22	Day 148 to Day 154	5 ^b	5 ^b	5 ^b	5 ^b	5 ^b	5 ^b	5 ^b	5 ^b	5 ^b	NA ^b

Table 6-4: Recommended corticosteroid tapering schedule

Week	Day	Corticosteroid dose ^a (mg/day; prednisone equivalent)											
23	Day 155 to Day 161	5 ^b	5 ^b	5 ^b	5 ^b	5 ^b	5 ^b	5 ^b	5 ^b	5 ^b	5 ^b	NA ^b	NA ^b
24	Day 162 to Day 168	5 ^b	5 ^b	5 ^b	5 ^b	5 ^b	5 ^b	5 ^b	5 ^b	5 ^b	5 ^b	NA ^b	NA ^b

NA=not applicable

^a Corticosteroid tapering is only required in those study participants receiving continuous corticosteroids at doses >7.5/day prednisone equivalent at the time of enrollment into the study.

^b Study participants starting at or achieving a dose of 7.5mg/day or lower may remain on this dose or taper at the discretion of the Investigator. This is indicated by cells with light grey font.

^c Alternating dosing every other day recommended to allow slow reduction based on standard tablet sizes

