10 SUPPORTING DOCUMENTATION AND OPERATIONAL CONSIDERATIONS

10.1 Appendix 1: Regulatory, ethical, and study oversight considerations

10.1.1 Regulatory and ethical considerations

The study will be conducted under the auspices of an IRB/IEC, as defined in local regulations, International Council on Harmonisation-Good Clinical Practice (ICH-GCP), and in accordance with the ethical principles that have their origin in the Declaration of Helsinki.

The Investigator/UCB will ensure that an appropriately constituted IRB/IEC that complies with the requirements of the current ICH-GCP version or applicable country-specific regulations will be responsible for the initial and continuing review and approval of the clinical study. Prior to initiation of the study, the Investigator/UCB will forward copies of the protocol, ICF, IB, Investigator's curriculum vitae (if applicable), advertisement (if applicable), and all other participant-related documents to be used for the study to the IRB/IEC for its review and approval.

Before initiating a study, the Investigator will have written and dated full approval from the responsible IRB/IEC for the protocol.

The Investigator will also promptly report to the IRB/IEC all changes in the study, all unanticipated problems involving risks to participants or others, and any protocol deviations, to eliminate immediate hazards to participants.

The Investigator will not make any changes in the study or study conduct without IRB/IEC approval, except where necessary to eliminate apparent immediate hazards to the participants. For minor changes to a previously approved protocol during the period covered by the original approval, it may be possible for the Investigator to obtain an expedited review by the IRB/IEC as allowed.

As part of the IRB/IEC requirements for continuing review of approved studies, the Investigator will be responsible for submitting periodic progress reports to the IRB/IEC (based on IRB/IEC requirements), at intervals appropriate to the degree of participant risk involved, but no less than once per year. The Investigator should provide a final report to the IRB/IEC following study completion.

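### Protocol Table 6-4 tapers a 35 mg starter one step ahead of the identical 40 and 30 mg columns, giving lower scheduled doses in Weeks 2, 4 and 6 (140 mg in all) with no stated reason

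*Protocol*

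**What the plan says.** Protocol Section 6.5.1.1 makes a taper mandatory above 7.5 mg/day prednisone equivalent, to start no later than Week 8, and aims for 7.5 mg/day or lower by Week 18. Table 6-4 is the recommended schedule. Its columns run from a 40 mg starting dose on the left, then 35, 30, 25 and 20 mg, down to 0.

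Three rows carry the point. In each, the first five doses belong to the 40, 35, 30, 25 and 20 mg columns:

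- Week 2: "Day 8 to Day 14 30 20 30 25 20"
- Week 4: "Day 22 to Day 28 20 15 20 20 20"
- Week 6: "Day 36 to Day 42 15 10 15 15 15 10" (the sixth value is the 15 mg column)

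For a screening dose that is not in the table, "the tapering regimen of the next higher dose in the table should be used". The schedule is flexible: if the Investigator thinks the pace too rapid, "a slower tapering regimen can be used". Footnote b says that participants at 7.5 mg/day or lower "may remain on this dose or taper at the discretion of the Investigator". The only remark on high doses is general: "In case of a high corticosteroid dose (>20mg/day) an early start of tapering should be considered".

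**The concern.** A default taper should not give a participant who enters on more steroid a lower dose than one who enters on less, unless there is a reason. Here the 35 mg column lies between two identical columns and is lower than both. On Day 8 a 35 mg starter goes to 20 mg, while a 30 mg starter stays on 30 and a 25 mg starter on 25. In Week 4 the 35 mg starter is on 15 mg and the 20 mg starter still on 20. The next-higher-dose rule extends this to every screening dose above 30 and below 35 mg, so a participant on 32.5 mg is also scheduled below a 30 mg starter from Day 8.

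What is at stake is the soundness of the sponsor's only stated default for the pace of a mandatory taper, for a narrow band of starting doses.

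**Working it through.** **Inputs.** All doses are mg/day from Table 6-4. Where the table alternates two doses on successive days I use the mean: 10/7.5 = 8.75 and 7.5/5 = 6.25. Weekly dose = daily dose × 7.

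**The plan's own target.** The 40 and 30 mg columns first reach 7.5 mg in Week 14 and the 35 mg column in Week 13. All meet the Week 18 aim, so no stated target fails.

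**The columns in full.**

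- 40 and 30 mg (identical): 30, 30, 20, 20, 15, 15, 10, 10, 10 in Weeks 1–9; 10/7.5 in Weeks 10–13; 7.5 in Weeks 14–17; 7.5/5 in Weeks 18–21; 5 in Weeks 22–24.
- 35 mg: 30, 20, 20, 15, 15, 10, 10, 10 in Weeks 1–8; 10/7.5 in Weeks 9–12; 7.5 in Weeks 13–16; 7.5/5 in Weeks 17–20; 5 in Weeks 21–24.

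From Week 2 on, each 35 mg cell equals the 40 mg cell of the following week. The 35 mg column is the same sequence with one of the two 30 mg weeks removed. The 25 and 20 mg columns differ from the 40 mg column only in Weeks 1 and 2.

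**Weeks in which the 35 mg column is lower than the 40 and 30 mg columns** (it is never higher):

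| Week | 40 and 30 | 35 | 25 | 20 | Footnote b on 35 mg cell | Gap to 40 and 30 over the week |
|---|---|---|---|---|---|---|
| 2 | 30 | 20 | 25 | 20 | no | 10 × 7 = 70 mg |
| 4 | 20 | 15 | 20 | 20 | no | 5 × 7 = 35 mg |
| 6 | 15 | 10 | 15 | 15 | no | 5 × 7 = 35 mg |
| 9 | 10 | 10/7.5 | 10 | 10 | yes | 1.25 × 7 = 8.75 mg |
| 13 | 10/7.5 | 7.5 | 10/7.5 | 10/7.5 | yes | 1.25 × 7 = 8.75 mg |
| 17 | 7.5 | 7.5/5 | 7.5 | 7.5 | yes | 1.25 × 7 = 8.75 mg |
| 21 | 7.5/5 | 5 | 7.5/5 | 7.5/5 | yes | 1.25 × 7 = 8.75 mg |

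- Weeks without footnote b: 70 + 35 + 35 = 140 mg.
- Weeks with footnote b: 4 × 8.75 = 35 mg.
- All weeks: 140 + 35 = 175 mg. Check: dropping one 30 mg week and adding one 5 mg week at the end gives (30 − 5) × 7 = 175 mg.

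**Totals over Weeks 1–24.** 40 and 30 mg columns: (30+30+20+20+15+15+10+10+10 + 4×8.75 + 4×7.5 + 4×6.25 + 3×5) × 7 = 1855 mg. 35 mg column: (30+20+20+15+15+10+10+10 + 4×8.75 + 4×7.5 + 4×6.25 + 4×5) × 7 = 1680 mg. The difference is 175 mg, or 175/1855 = 9.4%. The 25 and 20 mg columns total 1785 and 1715 mg, so the 35 mg column is below both.

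**Average fall from starting dose to 7.5 mg.** From 40 mg: 32.5/13 = 2.50 mg/week. From 35 mg: 27.5/12 = 2.29. From 30 mg: 22.5/13 = 1.73.

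**Could this be damage from reading the PDF?** Not for the cells that matter. In the copy I used, the rows for Weeks 1–12 hold 11 values for 11 starting doses, and Weeks 2, 4 and 6 are among them. Rows for Weeks 13–22 show 10 values and rows for Weeks 23–24 show 12. The left-hand columns run on consistently from Week 12, and from Week 22 every column compared here reads 5, so these columns are unaffected.

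**The case against.** The best case against has four parts.

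- **Footnote b.** A reader might count seven discrepant weeks, or five by setting aside only Weeks 17 and 21. The table does not support either as a firm count. The 35 mg cells in Weeks 9 and 13 also carry footnote b. Whether that mark frees an alternating 10/7.5 week is arguable, but the safe count is Weeks 2, 4 and 6. This stands, and the 140 mg figure reflects it.
- **No stated rule is broken.** The protocol nowhere says that scheduled doses must follow starting-dose order, no column has a rationale, and average pace does rise with starting dose (1.73, 2.29, 2.50 mg/week). This stands in part. A reader who infers that the 35 mg taper is faster than the 40 mg taper would be wrong on average pace; it is earlier at each step and lower in total. But the advice on early tapering covers every dose above 20 mg/day, and the amendment history's aim for Amendment 1, to start high-dose tapering promptly, applies at least as much to 40 mg. Neither explains why 35 mg alone is out of line.
- **The intended column is unknown.** The slip could lie in the slower columns. This is fair, and the sponsor should confirm. With the other columns kept, though, only one setting of the 35 mg column preserves dose order.
- **Limited force.** The table is recommended, its speed is adapted to the participant, and the taper may start as late as Week 8. The calendar-week gaps therefore arise only if a participant starts on Day 1 and follows the table literally. This stands, and it keeps the point minor.

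**Conclusion.** The 35 mg column departs from its neighbours without explanation. The firm size is 140 mg over Weeks 2, 4 and 6, with a largest gap of 10 mg/day in Week 2. A further 35 mg falls in weeks marked with footnote b. The figures assume a taper started on Day 1, followed as tabulated, with alternating doses averaged.

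A reader might go on to infer bias in the primary endpoint, through escape steroid use, or in the steroid-reduction endpoints. The documents do not support that. Both arms use the same table, Investigators may taper more slowly, and the number of participants entering above 30 and up to 35 mg is not given. The finding is a minor correction to a dosing default.

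**What to change.** Ask the sponsor to confirm the intended schedule. Unless there is an undocumented reason, set the 35 mg column to 30, 30, 20, 20, 15, 15, 10, 10, 10 in Weeks 1–9, 10/7.5 in Weeks 10–13, 7.5 in Weeks 14–17, 7.5/5 in Weeks 18–21 and 5 from Week 22. Because the 40 and 30 mg columns are identical, this is the only setting that restores dose order with the rest of the table unchanged. It also corrects the schedule for screening doses above 30 and below 35 mg. If the faster 35 mg pace was intended, the 30, 25 and 20 mg columns would have to come down instead.

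The cost is one table column, bundled with the next amendment. Protocol Section 10.1.1 states "The Investigator will not make any changes in the study or study conduct without IRB/IEC approval" (apart from immediate hazards), and the synopsis plans about 230 sites in about 31 countries, so a stand-alone amendment is not warranted. The Week 18 target, Investigator discretion and the analysis stay as they are. If all participants have already passed the taper weeks, which the documents do not say, the change no longer affects dosing in this trial.

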6.5.1.2 Antimalarials

Antimalarials (eg, hydroxychloroquine, chloroquine, and quinacrine) are permitted during the study (see inclusion criteria and maximum dose restrictions in [Table 6-5](#)).

Treatment with antimalarials must have been started or stopped at least 12 weeks prior to screening visit (V1). In study participants receiving concomitant antimalarials used for the treatment of SLE, doses must have been stable for at least 8 weeks prior to screening visit (V1) and should be kept stable through the study. Increases in doses of antimalarials are not permitted during the study, unless absolutely clinically indicated (dose reductions are allowed, if medically indicated [eg, due to toxicity], per the Investigator's discretion). Investigators are advised to contact the Medical Monitor or Sponsor's Study Physician, upfront if possible, to discuss the potential impact on the further study conduct in case a dose change is needed.

Table 6-5: Maximum doses of permitted concomitant antimalarials

Antimalarial (generic name)	Maximum dose allowed
Hydroxychloroquine	400mg/day
Chloroquine	500mg/day
Quinacrine	200mg/day
Quinine	Any dose allowed

Antimalarial blood levels will be measured at Screening and at selected visits during the study to serve as source for drug intake adherence in order to verify the documented dose of antimalarials.

If blood levels are inconsistent with the dose taken as reported by the participant this must be discussed with the participant and documentation of concomitant antimalarials must be adapted accordingly. In this case eligibility of the study participant must be reevaluated with respect to if the study participant indeed took a stable antimalarial dose as described in inclusion criterion 2.e3. If the dose is not considered as stable in the past 8 weeks prior to screening the study participant is not eligible at this time point.

In case a participant reports based on the conversation about antimalarial blood levels to have stopped or reduced intake of antimalarials due to intolerance more than 12 weeks before Screening, the actual intake needs to be documented appropriately. Based on the adequately documented concomitant medications it must be evaluated if the participant fulfills the inclusion criterion 2.e3. and no exclusion criterion before randomization. In case the participant is eligible they should be clearly instructed not to restart or increase antimalarial intake in this case.

Investigators are advised to contact the Medical Monitor or Sponsor's Study Physician upfront, if possible, to discuss the potential impact on the further study conduct in case a dose change is needed.

In case blood levels suggest a change in intake during the study, which was not reported by the participant, this should be discussed with the participant and the true intake should be documented on the concomitant medication page.

6.5.1.3 Other immunosuppressants/immunomodulatory agents

Other immunosuppressant or immunomodulatory agents are permitted during the study (see inclusion criteria and maximum dose restrictions in [Table 6-6](#)).

In study participants receiving concomitant immunosuppressants for the treatment of SLE, doses must have been stable for at least 12 weeks prior to the screening visit (V1) and should be kept stable through the study. If immunosuppressants permitted during the study were stopped before study entry, they must have been stopped no later than 8 weeks prior to the Screening Visit. Increases in doses of immunosuppressant or immunomodulatory agents are not permitted during the study, unless absolutely clinically indicated, per the Investigator's discretion but should not occur between Week 44 and Week 48. A temporary hold or dose reduction is allowed if medically indicated (eg, due to vaccination [ACR 2021] or due to toxicity), per the Investigator's discretion. Investigators are advised to contact the Medical Monitor or Sponsor's Study Physician, upfront, if possible, to discuss the potential impact on the further study conduct in case a dose change is needed.

Table 6-6: Maximum doses of permitted concomitant immunosuppressants

Immunosuppressant (generic name)	Maximum dose allowed
Azathioprine	300mg/day oral
Mycophenolate mofetil (including mycophenolate mofetil hydrochloride)	3000mg/day oral
Coated mycophenolate sodium	2200mg/day
Leflunomide	40mg/day oral
Methotrexate	25mg/week any route
Cyclosporine	4mg/kg/day
Voclosporin	47.4mg/day
Tacrolimus	3mg/day

Caution should be exercised in the co-administration of calcineurin inhibitors (cyclosporine and voclosporin) and the study drug. Local guidance(s) should be followed regarding monitoring of plasma levels when calcineurin inhibitors are administered. Additionally, when calcineurin inhibitors are administered concomitantly with DZP, special benefit-risk considerations and enhanced monitoring for infections are advised since the potential for synergistic immunomodulatory effects on T-cells (affecting both efficacy and safety) cannot be excluded. Please refer to Section [7.1.3](#) regarding recommended temporary discontinuation of study drug in case of infection.

It cannot be excluded that mycophenolate mofetil (MMF) could reduce effectiveness of combined hormonal contraceptives including levonorgestrel. Investigators are advised to regularly counsel patients who are of childbearing potential on the risk of MMF treatment for adverse pregnancy outcomes and the possibility of reduced effectiveness of hormonal contraceptives due to interaction with MMF. Please refer to Section [10.4](#) for further information.

6.5.1.4 Analgesics, medications including natural or synthetic cannabinoids (approved in line with local regulations), NSAIDs, HMG-CoA reductase inhibitors (statins), ACE inhibitors, and other anti-hypertensive drugs.

Study participants should stay on stable doses of the following other concomitant medications for the treatment of SLE during the study including the Screening Period, unless changes in these treatments are clinically indicated: analgesics, NSAIDs, medications including natural or synthetic cannabinoids (approved in line with local regulations), HMG-CoA reductase inhibitors (statins), ACE inhibitors, and other anti-hypertensive drugs.

